3.2 Phase I

Phase I is designed to test a novel healthcare practice-based exercise regimen for SWPF testing of PAPRs with 25 evaluable subjects that represent the US workforce facial measurements. In this phase, subjects will not wear PAPRs, however they will complete one 30-minute regimen that includes ten, 3-minute exercises to determine Work Rate category allocation per exercise. The simulated workplace exercises were created based on: a) exercises from ANSI (American National Standards Institute) and OSHA respirator test protocols (ANSI, 2010; CFR, 1998); and b) routine healthcare activities (Table 3.). This phase will be completed without PAPRs and subjects will have physiological measurements taken with a metabolic cart. During each exercise regimen replicate subjects will be equipped with a heart rate (HR) monitor and siliconerubber oronasal facemask from the metabolic cart. Expired air sample will be analyzed for oxygen uptake (VO₂), minute ventilation (V_e), and carbon dioxide (VCO₂).

25 subjects x 1 regimen x 3 replicates = 75 max oxygen uptake (VO₂) and 75 max heart rate (HR) values per exercise to determine work rate category allocation (Table 4.). In this study phase, the data will be analyzed after all 25 subjects complete the first of three attempts so that each exercise will have 25 values calculated. Subjects will complete all consent and screening items, along with the first replicate of Phase I during their first visit (~3 hours) and will complete the second and third replicates on a different visit (~3 hours). Phase I will be conducted in conjunction with screening and completed over 2 visits (~6 hours total). It is anticipated that all subjects will complete Phase I/screening in 3-6 months (July 2019-December 2019).

Mean Population Parameter with 95% (1.960) confidence interval will be used to analyze data. For each exercise, if the 95% confidence interval is within theoretical bounds for each work rate, then the second and third replicates will not need to be completed and Phase II of this study will begin. The theoretical bounds can be found under the relative intensity columns in Table 4.

Hypothesized Work Rates

The 10-exercise regimen includes hypothesized light, moderate, and hard work rates. These work rates will be verified during Phase I using a metabolic cart. Average values for work rate will be calculated for each exercise across all individuals test data. The hypothesized work rates in Table 3 will be determined and verified and /or modified for regimen use in Phase II.

These hypothesized work rates will also dictate the order in which the exercise regimen is performed during Phases I and II. Exercises will be selected from Table 3 and performed in the following sequence, with gradually building intensity; 1) light, 2) moderate, and 3) hard. A short break will be given to subjects following a hard exercise to allow the subject's heart rate to return to within 20 bpm of the initial baseline value (~ 10 minutes). They will repeat this sequence (light, moderate, hard, break) once more with three different exercises from Table 3, and then a third time with the remaining four exercises (this time with two light exercises), which will conclude the test.

This sequence was established for subject safety reasons and scientific reasons; 1) to avoid a "carry-over" effect between exercises (i.e. a more intense exercise affecting measurements of the following exercise), 2) to increase the likelihood of subjects completing the full 3 minutes of exercise, and 3) it is less physically demanding to the subjects.

Table 3. Exercise Regimen

Exercise #	Test exercise	Approximate Duration (min)	Hypothesized Work Rate
1	Normal breathing: normal breathing while standing	3	Light
2	Reading: reading the rainbow passage while standing	3	Light
3	Moving head side-to-side: moving head side-to-side at approximately 10 times/min while standing	3	Light
4	Moving head up and down: moving head up and down at approximately 10 times/min while standing	3	Light
5	Twisting at waist with weight: Twisting at waist to the left while holding with both hands a 10-lb bag equipped with a handle, raising and lowering arms and then repeat this to the right, at a rate of 12-15 sets/min.	3	Moderate
6	Reaching up and stepping out (Modified jumping jack): bending the left knee slightly while reaching up both arms overhead & looking up and stepping the right leg out to the side, then repeat with the other leg, at a rate of 10-12 sets/min.	3	Moderate
7	Walk on a treadmill: walking upright on a treadmill at a speed of 3 mile/h without movement of the head, and without speech.	3	Moderate
8	Bending and Picking up weight: bending to pick up two weighted bags equipped with a handle (5-lb bag/each hand) and carrying them from side-to-side of the testing chamber at a moderate walking pace, then bending to put down weights. Repeat for 3 minutes.	3	Hard
9	Perform CPR/AED: perform CPR on a training manikin by compressing chest cavity ~1.5 - 2 inches at a rate of 80-100 compressions/min. 2 min of CPR followed by 1 minute of AED use.	3	Hard

10	Stair climbing: stair climbing (using a 3-step ladder) climb rate ~ 10-12 cycles/min (one cycle = up 3 steps and back down 3 steps).	3	Hard	
----	---	---	------	--

362

363 364 365

366 367 368

369 370

371

372

382

387 388 389 Work Rates

Average work rates will be determined for each individual exercise for each subject, and the mean values will be then calculated for each exercise for all 25 test subjects. Work rate classifications are listed in Table 4 below (American College of Medicine, 2013).

Table 4. Work Rate Classifications for Physical Activities

	Relative Int	ensity	Absolute Intensity Ranges (METs) Across Fitness Levels			
Intensity	VO₂R (%) HRR (%)	Maximal HR (%)	12 MET VO _{2max}	10 MET VO _{2max}	8 MET VO _{2max}	6 MET VO _{2max}
Very light	<20	<50	<3.2	<2.8	<2.4	<2.0
Light -	20-39	50-63	3.2-5.3	2.8-4.5	2.4-3.7	2.0-3.0
Moderate	40-59	64-76	5.4-7.5	4.6-6.3	3.8-5.1	3.1-4.0
Hard (vigorous)	60-84	77-93	7.6-10.2	6.4-8.6	5.2-6.9	4.1-5.2
Very hard	≥85	≥94	≥10.3	≥8.7	≥7.0	≥5.3
Maximal	100	100	12	10	8	6

The information from the GXT (Appendix K) has a screening purpose and a research purpose. It will be used for 1) safety screening prior to participation and establishment of test termination criteria (Section 7.4) and 2) relative workload determination for the desired work-related activity in Table 3. Work rates in Table 4 will be determined for each exercise as a percentage of the subjects' maximum oxygen uptake and maximum heart rate, both of which are measured during

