8.0 STATISTICAL METHODS

8.1 Phase I Statistical Methods

For Phase I, mean VO₂ and HR values with 95% confidence interval will be calculated for each exercise. In this study phase, the data will be analyzed after all 25 subjects complete the first of three replicates so that each exercise will have 25 values calculated. If, after the first 25 subjects, the lower and upper bounds of the 95% confidence interval for the estimated population parameters are within the theoretically categorized work rates, then second and third replicates will not be needed.

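### The Phase I interval uses the normal multiplier 1.960 where 25 subjects call for t(24) = 2.064, and Section 3.2 leaves unclear how three replicates would be combined: a minor error with a one-line fix

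*Protocol*

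**What the plan says.** **Interval.** Section 3.2 of the protocol fixes both the method and the multiplier: "Mean Population Parameter with 95% (1.960) confidence interval will be used to analyze data". Section 8.1 repeats the 95% interval but names no multiplier.

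**Timing of the look.** Section 3.2: "the data will be analyzed after all 25 subjects complete the first of three attempts so that each exercise will have 25 values calculated". Section 8.1 agrees: "after all 25 subjects complete the first of three replicates so that each exercise will have 25 values calculated". The data-analysis footnote to the Phase I calendar in Appendix A also places the interim analysis after replicate 1.

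**Rule.** The bounds are the relative-intensity columns of Table 4. Section 8.1 says that if both limits of the interval "are within the theoretically categorized work rates, then second and third replicates will not be needed". Section 3.2 adds that Phase II then begins.

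**Replicates.** Section 3.2 counts "25 subjects x 1 regimen x 3 replicates = 75 max oxygen uptake (VO₂) and 75 max heart rate (HR) values per exercise" and says that these serve to allocate the work-rate category. Under Hypothesized Work Rates, the same section averages over the test data of all individuals. Under Work Rates it takes an average per subject and then a mean over the group of 25: "Average work rates will be determined for each individual exercise for each subject, and the mean values will be then calculated for each exercise for" (the sentence goes on to name that group).

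**The concern.** The figure 1.960 is the normal quantile, which is exact only when the SD is known. Here the SD comes from the same 25 values, so the interval is narrower than its label says. It is also the only stated criterion for dropping replicates 2 and 3. The classes it supports set the exercise order (Section 3.2), carry into Phase II (Section 3.3) and define the Phase III regimens (Section 3.4). Work rate is one of the two primary objectives (Section 2.1).

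The second question arises only if replicates 2 and 3 are run. Three repeats on one person are correlated. An analyst who took 75 as the sample size would get an interval that is clearly too narrow, for exactly those exercises that the first look had left unresolved.

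**Working it through.** **1. The plan's own figures.** The two-sided 95% normal quantile is 1.95996, which rounds to 1.960. The count is 25 × 1 × 3 = 75. Both reproduce.

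**2. Correct multiplier at the stopping look.** There are n = 25 values, one per subject, and the SD is estimated, so df = 24 and t(0.975, 24) = 2.064.
- Ratio: 2.064 / 1.960 = 1.053. The correct interval is 5.3% wider; equivalently, the planned one is 1 − 1.960 / 2.064 = 5.0% too narrow.
- True coverage with 1.960: 2·F(1.960) − 1 = 0.938, where F is the t distribution function on 24 df.

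**3. Size on the measurement scale.** The protocol gives no SD for the Phase I percentages. Values of 5, 8 and 10 points are assumed. Half-width = multiplier × SD / √25:

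| Assumed SD | with 1.960 | with 2.064 | difference |
|---|---|---|---|
| 5 | 1.96 | 2.06 | 0.10 |
| 8 | 3.14 | 3.30 | 0.17 |
| 10 | 3.92 | 4.13 | 0.21 |

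By their printed limits, the Light, Moderate and Hard bands in Table 4 span 12 points (64–76% of maximal HR) to 24 points (60–84% of VO₂R or HRR).

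**4. Effect on the rule.** With the true mean on the lower band limit and the upper limit far away, the rule passes with probability P(t24 > multiplier). That is (1 − 0.938) / 2 = 3.1% with 1.960 and 2.5% with 2.064. Inside the band, simulation (100,000 runs, normal data, n = 25, bands 40–59 and 64–76, the SDs above) shows the chance of passing raised by 0 to about 5 percentage points. For example, with band 40–59, SD 8 and true mean 43, it is 47.3% against 43.4%.

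**5. If 75 values were pooled as independent.** This applies only to an interval formed after all three replicates. The within-subject correlation ρ is not in the protocol; 0.5 to 0.9 is assumed. The variance of the mean is (s²/75)(1 + 2ρ), so:
- the SE is understated by the factor √(1 + 2ρ);
- the effective n is 75 / (1 + 2ρ);
- coverage with 1.960 is about 2·F(1.960 / √(1 + 2ρ)) − 1, on 24 df;
- the true fall in SE from one to three replicates is 1 − √((1 + 2ρ)/3), against an apparent fall of 1 − 1/√3 = 42%.

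| ρ | SE understated by | effective n | coverage | true fall in SE |
|---|---|---|---|---|
| 0.5 | 1.41 | 37.5 | 82% | 18% |
| 0.7 | 1.55 | 31.3 | 78% | 11% |
| 0.9 | 1.67 | 26.8 | 75% | 3% |

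**The case against.** The strongest reply is that the effect of the multiplier is negligible: 0.1 to 0.2 points of half-width against bands of 12 points or more. A wrong pass would only skip two repeats of an exercise test done without a respirator. Section 8.1 names no multiplier, so an analysis plan that used t would be consistent with it. The smallness is granted. But Section 3.2 prints the wrong constant, so this is not a detail left open for the analysis plan.

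A reader might infer something stronger: that the rule for stopping replication itself runs on 75 correlated values. The protocol does not support that. Sections 3.2 and 8.1 and Appendix A all place the look after the first replicate, with one value per subject, so n = 25 is right and replicate correlation does not enter. Nor is the rule said to be applied again after replicates 2 and 3.

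A reader might also infer that an interval with n = 75 is planned. No sentence says so. The 75 is a correct count of measurements, and the text under Work Rates describes an average per subject followed by a mean over 25 subjects, which is the sound structure. What remains is looseness: that text mentions neither replicates nor the interval, while two other statements in Section 3.2 (75 values to allocate the category, and averages over all individuals' data) could be read as pooling. An analysis plan that is not shown here may settle this.

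**Conclusion.** The multiplier in Section 3.2 is wrong as written. For 25 subjects with an estimated SD it should be 2.064. The interval is about 5% too narrow, coverage is 93.8%, and the pass rate on a band limit is about 3.1% instead of 2.5%. These results assume roughly normal values; the half-widths and the simulated pass rates inside the band also rest on assumed SDs of 5 to 10 points.

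The 75-value issue is a conditional ambiguity, not an established error. It matters only for an interval or classification made after all three replicates, and the factors 1.41 to 1.67 hold only if the values are pooled as independent and the correlation is 0.5 to 0.9. Taken together, the point is minor.

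**What to change.** In Section 3.2, replace 1.960 with the t quantile on n − 1 degrees of freedom (2.064 for n = 25), and name the same quantile in Section 8.1. In both places, add that any interval using more than one replicate is based on subject averages (n = 25, 24 df) or on a mixed model with a random subject effect. Keep 75 in Section 3.2 as the number of planned measurements, and say that it is not the sample size for the interval.

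The cost is a sentence in each section. Intervals become slightly wider. Under the assumed SDs, an exercise would miss the rule at the first look up to about 5 percentage points more often, so replicates 2 and 3 become a little more likely. The change itself requires no extra subjects and no visits beyond those already in the calendar.

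### Five of the six moderate and hard exercises have a loose pace that is neither held nor recorded, so work may differ between the two flow rates without anyone knowing

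*Protocol*

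**What the plan says.** Section 3.2, Table 3, defines the ten exercises used in Phases I and II. For the six classed as moderate or hard, the pace is given as follows:

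- Exercise 5, twisting with weight (moderate): "at a rate of 12-15 sets/min".
- Exercise 6, reaching and stepping (moderate): "at a rate of 10-12 sets/min".
- Exercise 7, treadmill (moderate): "walking upright on a treadmill at a speed of 3 mile/h", a single fixed speed.
- Exercise 8, bending and carrying (hard): "at a moderate walking pace", with no number.
- Exercise 9, CPR/AED (hard): "at a rate of 80-100 compressions/min", for two of the three minutes.
- Exercise 10, stairs (hard): "climb rate ~ 10-12 cycles/min".

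The light exercises have one nominal pace (3 and 4) or none (1 and 2). Table 6 in Section 3.4 repeats the ranges for exercises 6, 9 and 10 in Phase III.

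Work rate is measured by metabolic cart in Phase I, without a PAPR (Section 3.2). Section 3.3 carries those work rates into Phase II. Monitoring described for Phases II and III consists of oxygen saturation, differential pressure and CO2 (Section 3.3), plus a heart-rate stopping criterion (Section 7.4, Table 7). The test procedures in Sections 5.2 and 5.3 mention no pacing device, no record of pace and no rule to keep pace equal between flow settings.

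**The concern.** Section 2.1 names two primary objectives: the relation of flow rate to SWPF, and the relation of work rate to SWPF. The first needs each subject to do the same work at both flows. The second needs the work actually done to be known.

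Pace is under the subject's control and may respond to the condition under test. Section 7.5 lists difficulty breathing as a possible, rare consequence of lower flow. A subject who eases off at the reduced flow needs less air. On the literature review in Section 1.2, lighter work meant less penetration in both loose-fitting facepieces studied. The easing-off would then offset part of any loss of protection from the lower flow, and the result would lean towards the finding that protection is maintained. For a study that may support lower certified flows, that is the unsafe direction of error.

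The overall SWPF is a harmonic mean over exercises (Sections 3.3 and 8.2), so the lowest exercise values weigh most. If the harder exercises give the lowest values, which is plausible but not stated, the outcome depends most on the exercises whose pace is least controlled.

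**Working it through.** **Step 1: which exercises are affected.** Table 3 classes 5, 6 and 7 as moderate and 8, 9 and 10 as hard. Only exercise 7 has a fixed pace. Five of six are affected, including all three hard ones. Of these five, 6, 9 and 10 recur in Phase III.

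**Step 2: width of the ranges.** Rise from slow to fast = high/low − 1. Permitted slowing = 1 − low/high.

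| Exercise | Range per minute | Slow to fast | Fast to slow |
|---|---|---|---|
| 5 | 12 to 15 | 15/12 − 1 = 25% | 1 − 12/15 = 20% |
| 6 | 10 to 12 | 12/10 − 1 = 20% | 1 − 10/12 = 16.7% |
| 9 | 80 to 100 | 100/80 − 1 = 25% | 1 − 80/100 = 20% |
| 10 | 10 to 12 | 12/10 − 1 = 20% | 1 − 10/12 = 16.7% |
| 8 | none given | cannot be computed | cannot be computed |

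For exercise 9 the range governs the compressions only: two of three minutes in Table 3, four of five in Table 6.

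**Step 3: would slowing be noticed?** In Phases II and III the stated measurements are oxygen saturation, differential pressure, CO2 and a heart-rate limit for stopping. None records pace or oxygen uptake. Section 8.2 enters work rate or exercise regime as a factor, which is the planned category and not the work delivered. A difference in pace between flows would leave no trace for the analysis to adjust.

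**Step 4: does the range reach across the moderate/hard cut?** First, the plan's own figure. Table 4 puts the start of hard work at 60% VO2R. In METs this is 1 + 0.60 × (max − 1), which gives 7.6, 6.4, 5.2 and 4.0 for maxima of 12, 10, 8 and 6. Table 4 prints 7.6, 6.4, 5.2 and 4.1, so it is reproduced to within 0.1.

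Now assume that intensity above rest varies as pace to the power e. The documents give no such relation, so e is shown over a range. An exercise in the hard band at the fast end falls below 60% at the slow end if its fast-end intensity is under 60 × (high/low)^e. The share is (threshold − 60)/25, taking the hard band as 60 to 85.

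| e | 20% range: threshold (share of band) | 25% range: threshold (share of band) |
|---|---|---|
| 1 | 72.0% (48%) | 75.0% (60%) |
| 0.5 | 65.7% (23%) | 67.1% (28%) |
| 0.25 | 62.8% (11%) | 63.4% (14%) |

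Under proportionality (e = 1), 70% at the fast end becomes 70/1.20 = 58.3% or 70/1.25 = 56.0% and crosses; 80% becomes 66.7% or 64.0% and does not. The hard band spans a ratio of 84/60 = 1.40, wider than 1.20 or 1.25, so exercises in its upper part stay hard. Crossing therefore depends on where each exercise lies, and the protocol gives no intensity for any of them.

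**The case against.** A reader might infer that pace alone moves exercises from hard to moderate. The documents do not support that. It needs an exercise near 60% VO2R and an assumed link between pace and uptake. Phase I also classifies on the mean of 25 subjects, with a check that the 95% confidence interval lies within the Table 4 band (Sections 3.2 and 8.1), so an exercise close to the cut could well fail the check and be noticed. The Phase I label is not reassigned later; what can shift is the work delivered under it. This part of the objection stands.

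A reader might also infer a known bias across all PAPRs. The study reviewed in Section 1.2 found the work-rate effect in loose-fitting facepieces but not in the tight-fitting device on clean-shaven subjects. In Table 5, loose-fitting facepieces are two of eight models, and Section 1.3 calls the wider evidence inconclusive. This also stands: the direction is supported for that design only.

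Next, nothing shows that subjects will slow. Section 7.5 calls breathing difficulty rare and tells subjects to remove the device and inform staff; Section 5.3 has them signal when unable to continue. But these provisions concern subjects who stop. They do not cover one who carries on more slowly within the permitted range.

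Finally, the ranges are only about 9% (1/11) to 11% (1.5/13.5 and 10/90) either side of their midpoints, and Phase III lengthens exercises from three to five minutes, so equal pace would not guarantee the same work-rate class there. Both are fair. Neither bears on keeping pace equal within a subject between the two flows in Phase II.

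**Conclusion.** The point holds as a gap in control of the flow comparison. For exercises 5, 6, 9 and 10 the protocol permits slowing of 16.7% to 20%; for exercise 8 the permitted slowing is unbounded by any number. Nothing holds or records pace between flow rates, and delivered work is not measured by metabolic cart after Phase I.

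That this could hide a loss of protection rests on two assumptions: that some subjects slow at the reduced flow, and that lighter work lowers penetration. The protocol's own review supports the second for loose-fitting facepieces only. The documents give no basis for sizing the effect on SWPF, and a shift across the moderate/hard cut is a conditional possibility, not a finding.

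The change is worth making because pace that was neither fixed nor recorded during testing cannot be recovered by any later analysis.

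**What to change.** In Tables 3 and 6, state one target pace for each of exercises 5, 6, 9 and 10, chosen by the sponsor from within the present range, and a fixed crossing rate for exercise 8. Cue the pace with the same audible metronome at both flow rates and in all phases, and record the pace achieved in every test. The permitted range then shrinks to zero, as it already is for the treadmill.

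Keep tests in which the pace was not held in the primary analysis. Flag them and examine them in a sensitivity analysis. Excluding them could remove the very tests in which reduced flow was hardest to tolerate, since failure to hold pace may itself be an effect of the flow. The stopping criteria need no change.

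The cost is a metronome, edited table cells and some extra recording. The downside is slightly less natural movement.

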NIOSH BV Cell	Percentage of Population	No. of Test Subjects
1	5.5	2
2	5.3	2
3	10.5	2
4	25.0	5
5	7.1	2
6	5.7	2
7	21.3	4
8	8.7	2
9	5.2	2
10	3.5	2
Total	97.7	25

Fit Testing

Tight fitting PAPR models require an approved OSHA fit test to determine safe and protective seal for the user. To verify NIOSH/NPPTL cell category allocation accuracy, each subject will complete fit testing for all three tight fitting PAPRs to be used in Phase II of this study, even if a subject is anticipated to only participate in Phase I. For the tight-fitting PAPR fit tests, a 2% NaCl solution in distilled water will be used as a generator solution under room conditions (in a laboratory, but outside of a test chamber). A particle generator (Model 8026, TSI, Shoreview, MN) and an OSHA approved condensation nuclei count protocol with PortaCount Plus (Model 8038; TSI) will be used.

Maximal Graded Exercise Test (GXT)

Subjects will undergo a Maximal Graded Exercise Test according to the Bruce protocol (Appendix K) to further review medical eligibility and subject specific termination criteria, such as maximal heart rate, for this study. This test will also obtain physiological measurements

(maximal oxygen uptake and maximal heart rate) that will be used in Phase I calculations. This will take place in the NPPTL physiology lab using a treadmill and metabolic cart. It may also take place in the NPPTL Building 40 environmental test chamber and high bay area, which is also equipped with a treadmill and metabolic cart. See Appendix K for complete procedure and metabolic cart measurements.

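### Phase I computes oxygen uptake as a percentage of VO2max but grades it against Table 4 bounds set on the VO2-reserve scale, so the oxygen index can place an exercise one work-rate band too high

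*Protocol*

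**What the plan says.** Under Work Rates, Protocol Section 3.2 states: "Work rates in Table 4 will be determined for each exercise as a percentage of the subjects' maximum oxygen uptake and maximum heart rate". Both maxima come from the graded exercise test. Section 3.1 describes the measurements carried forward from that test as "maximal oxygen uptake and maximal heart rate) that will be used in Phase I calculations". Neither section, nor Section 8.1, names a resting oxygen uptake or a conversion to reserve.

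On the bounds, Section 3.2 says "The theoretical bounds can be found under the relative intensity columns in Table 4". Table 4 has two relative-intensity columns: one for VO2 reserve and heart-rate reserve together, and one for percentage of maximal heart rate. Four further columns give MET ranges for maxima of 12, 10, 8 and 6 METs. In that column order the rows read:

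- Light: "20-39 50-63 3.2-5.3 2.8-4.5 2.4-3.7 2.0-3.0"
- Moderate: "40-59 64-76 5.4-7.5 4.6-6.3 3.8-5.1 3.1-4.0"
- Hard: "60-84 77-93 7.6-10.2 6.4-8.6 5.2-6.9 4.1-5.2"
- Very hard: "≥85 ≥94 ≥10.3 ≥8.7 ≥7.0 ≥5.3"

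On the interval, Section 3.2 says "Mean Population Parameter with 95% (1.960) confidence interval will be used to analyze data". Sections 3.2 and 8.1 apply it after the first replicate, with 25 values per exercise. If the interval lies inside the band, replicates 2 and 3 are not run.

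**The concern.** The heart-rate half of the rule has a matching column in Table 4. The oxygen half does not: a percentage of VO2max is compared with cut-points that are percentages of VO2R. Below maximum, the first is always larger than the second for the same uptake, so any error goes one way, towards a higher band.

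Allocating each exercise to a band is the stated purpose of Phase I. The result decides whether replicates 2 and 3 are needed and whether Table 3's hypothesized work rates are confirmed or changed for Phase II. Section 3.4 also refers to it for Phase III. Work rate is a factor in the Section 8.2 and 8.3 models, and its relation to SWPF is primary objective b.

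**Working it through.** **Inputs.** Relative cut-points c = 0.20, 0.40, 0.60, 0.85 and the MET lower bounds, both from Table 4. M is the subject's maximum in METs. Resting uptake is not stated in the protocol; 1 MET is an assumption, tested in step 1 and varied in step 5.

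**1. Which scale is Table 4 on?** Lower bounds (light/moderate/hard/very hard):

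| M | Table 4 | Reserve: 1 + c(M − 1) | Percentage of maximum: cM |
|---|---|---|---|
| 12 | 3.2/5.4/7.6/10.3 | 3.2/5.4/7.6/10.35 | 2.4/4.8/7.2/10.2 |
| 10 | 2.8/4.6/6.4/8.7 | 2.8/4.6/6.4/8.65 | 2.0/4.0/6.0/8.5 |
| 8 | 2.4/3.8/5.2/7.0 | 2.4/3.8/5.2/6.95 | 1.6/3.2/4.8/6.8 |
| 6 | 2.0/3.1/4.1/5.3 | 2.0/3.0/4.0/5.25 | 1.2/2.4/3.6/5.1 |

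The reserve formula with a 1-MET rest matches all 16 bounds within 0.1 MET. The percentage-of-maximum formula misses by up to 0.8 MET. The VO2R heading is therefore not a misprint for VO2max.

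**2. Direction.** For an uptake of v METs, v/M − (v − 1)/(M − 1) = (M − v)/[M(M − 1)], which is positive for every v below M. No exercise can be moved down.

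**3. Size.** The reserve cut-points as percentages of VO2max are [1 + c(M − 1)]/M:

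| M | light | moderate | hard | very hard |
|---|---|---|---|---|
| 12 | 26.7 | 45.0 | 63.3 | 86.2 |
| 10 | 28.0 | 46.0 | 64.0 | 86.5 |
| 8 | 30.0 | 47.5 | 65.0 | 86.9 |
| 6 | 33.3 | 50.0 | 66.7 | 87.5 |

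The gap below each cut-point is 1 + c(M − 1) − cM = 1 − c, that is 0.8, 0.6, 0.4 and 0.15 MET at any fitness level. The gaps sum to 1.95 METs. As a share of the range from rest to maximum, 1.95/(M − 1) is 17.7% at 12 METs, 21.7% at 10, 27.9% at 8 and 39.0% at 6. These are shares of the intensity scale, not of the ten exercises.

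**4. Examples.**
- M = 10, uptake 4.5 METs: 45.0% of VO2max, so Moderate by the stated rule. On reserve, 3.5/9 = 38.9%, and Table 4's 10-MET column lists 4.5 as Light.
- M = 8, uptake 5.0 METs: 62.5% of VO2max, so Hard. On reserve, 4/7 = 57.1%, and the 8-MET column says Moderate.
- M = 10, uptake 5.0 METs: 50.0% of VO2max and 44.4% of reserve, Moderate both ways. This uptake lies outside the gaps.

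The replicate decision can change in either direction. Suppose, for illustration, that all subjects have M = 10. An interval of 4.5 to 5.0 METs is 45.0-50.0% of VO2max, inside Moderate, so replicates are skipped; on reserve it is 38.9-44.4% and straddles 40%. An interval of 3.5 to 4.5 METs is 35.0-45.0% of VO2max and straddles 40%; on reserve it is 27.8-38.9%, inside Light.

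**5. Sensitivity to resting uptake.** With rest at 0.8 to 1.2 MET and capacities of 6 to 12 METs, the cut-points lie at 25.3-36.0/44.0-52.0/62.7-68.0/86.0-88.0% of VO2max. All stay above 20/40/60/85, so the direction does not depend on the assumption.

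**6. Interval.** With 25 values (24 degrees of freedom) the multiplier for 95% is 2.064. Using 1.960 gives an interval 1.960/2.064 = 95% as wide, with 93.8% coverage.

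**The case against.** The protocol gives no oxygen uptake for any of the ten exercises, so none is shown to fall in a gap. Within a subject the two percentages rise together, so the intensity ranking of exercises does not change, and no SWPF measurement changes. Only a label can move, by one step. Heart rate is a second index on its proper scale, and nothing says that oxygen uptake governs. Section 3.2 uses the hypothesized work rates to set exercise order, and Table 6 already names the Phase III exercises with expected labels. The wording may also be shorthand: Appendix K says subjects are placed in a Table 4 category after the exercise test, which could mean the MET columns for the subject's own fitness.

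Most of this stands as a limit on the consequence. It does not remove the mismatch. Section 3.2 points to the relative-intensity columns, not the MET columns, and only VO2max and maximal heart rate are carried into Phase I calculations. An analyst following the text would compute VO2/VO2max.

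Three stronger readings are tempting but not supported:

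- A reader might infer that exercises are in fact misclassified. Without uptake values, the text supports only that they can be.
- A reader might infer that the oxygen and heart-rate indices will disagree systematically. That depends on how heart rate and oxygen uptake relate in these subjects, which the protocol does not give.
- A reader might infer from the count of 75 values per exercise that replicates are treated as independent. Section 3.2 only counts them there. Under Work Rates it averages within subject and then over 25 subjects, and the interval check uses 25 values.

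**Conclusion.** The oxygen rule is wrong as written: the index and its bounds are on different scales, and Table 4's own MET columns contradict the resulting labels. An exercise within 0.8, 0.6, 0.4 or 0.15 MET below the light, moderate, hard or very hard cut-point is placed one band too high by the oxygen index. Other exercises, and the heart-rate index, are unaffected. These sizes rest on the 1-MET rest inferred from Table 4; the upward direction does not. The mismatch can alter the decision on replicates 2 and 3 and the labels used in Phases II and III, but whether it does so for any of the ten exercises cannot be told from the protocol. Using 1.960 with 25 values is a true but minor point.

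**What to change.** In Section 3.2, with a matching line in Section 8.1:

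- Classify each subject's oxygen uptake as %VO2R = (VO2 − 1 MET)/(VO2max − 1 MET), and state the uptake taken as 1 MET. Equivalently, up to Table 4's rounding, use the MET bounds for the subject's own maximum, taking 1 + c(M − 1) where the maximum is not 6, 8, 10 or 12 METs.
- Keep percentage of maximal heart rate for the maximal-heart-rate column.
- State which index decides the band, and the replicate question, if the two disagree.
- Compute the interval from the 25 subject values with t on 24 degrees of freedom, 2.064.

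The cost is wording and one formula. Exercise uptake and VO2max are already collected, so no new measurement is needed with the 1-MET value. Some exercises may drop one band by the oxygen index.
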